10 STATISTICAL ANALYSES IMPLEMENTATION SPECIFICATIONS

This section contains the specifications required to implement the statistical methods for efficacy analyses described in Section 7 with a multiple imputation (MI) method for missing data. These specifications are given in sufficient detail such that an independent reviewer can replicate the efficacy analysis and results based on the methods described in Section 7 and the additional MI implementation specifications contained in this section.

These specifications incorporate the guidance for pre-specifying details of MI provided in ([O'Kelly & Ratitch, 2014](#)) Chapter 6. Multiple imputation procedures are implemented in a three step process: Step 1: Multiple Imputation, Step 2: Statistical Analyses, Step 3: Statistical Inference. Each of these steps are described for the MI procedures presented herein.

SAS® (SAS Institute), software Version 9 or higher will be used to implement all statistical methods, and to produce all Tables and Figures containing analyses results and summary descriptive statistics.

10.1 Declarations and Multiple Imputation Considerations

a) Random Number Seed: 07091993

A random number seed is specified for each invocation of an MI procedure in SAS. Specifying a seed enables the numeric results of the multiple imputation procedures to be reproduced.

b) Number of multiple imputations (M): **40**

This is the number of imputation datasets that will be generated for all imputation procedures. M=40 is chosen since the fraction of missing information, and the relative increase in variance, are anticipated to be small.

c) Discreteness of the efficacy variables

For the efficacy measures that occur only once post-baseline during the study at Week 24/ET, the endpoint value is Week 24/ET. For the following efficacy variables the Week 24/ET value is a discrete random variable: WPOV-E, WPOV-M, WPOV, LM, ZLM, and WZLM scores, QIDS total score, SIT scores. The MI method described below imputes the Week 24/ET value as a continuous variable. Consequently, imputed values will be real numbers; these imputed values will not be rounded to nearest integers as this may introduce bias and is not recommended ([O'Kelly & Ratitch, 2014](#)). For each of these efficacy variables, and including APOV, SF36v2 t-scores, and EQ-5D-5L VAS scores as well, imputation values obtained from the MI may be outside the defined range of the variable. If a value outside this range is obtained in the imputation, the imputed value will be truncated at the maximum or minimum value depending on which of these values it exceeds.

10.2 Multiple Imputation Method – PMM with J2C

As described in Section [7.1.3](#) for the treatment policy estimand, missing data due to study discontinuation will be imputed with a multiple imputation method (MI) for the following efficacy

variables: APOV, WPOV-E, WPOV-M, WPOV; LM, ZLM, and WZLM scores; SF36-v2 scores, QIDS total score, SIT score, and EQ-5D-5L VAS.

Multiple imputation with a PMM and J2C method will be conducted using the sequential modeling method as described in (O'Kelly & Ratitch, 2014), Chapter 7. To implement J2C method, first the initial dataset is used to impute missing data in the control group with multiple imputation under MAR assumption. The initial dataset used is the analysis dataset – in this case a dataset with a single post-baseline observation at Week 24/ET; this dataset is referred to as *EFF*. Therefore, MI is performed on a single post-baseline observation with missing data.

The statistical model used to estimate parameters in the imputation of missing data for analysis variable in the control group under MAR assumption includes the following terms: treatment, baseline covariate, nasal polyp status (present, absent), previous sinus surgery (Y, N). This model is implemented in PROC MI with MONOTONE REGRESSION statement. The output dataset is referred to as *EFF_MI_MAR*. This dataset, after some data manipulation to restore the missing data in the active active treatment arms, is the input dataset for implementation of J2C method in SAS, which involves three steps for imputing a single time point.

Step 1: Remove subjects in the active treatment groups with complete data at Week 24/ET (OUTPUT REST_V6). Keep remaining subjects (OUTPUT IMPUTE_V6):

- a) Subjects in active treatment groups with data to be imputed at Week 24/ET
- b) Control subjects with observed and multiply imputed data under MAR at Week 24/ET

Step 2: Multiple imputation of Week 24/ET missing data (INPUT IMPUTE_V6) using a regression of Week 24/ET analysis variable on baseline value of endpoint only (OUTPUT IMPUTED_V6).

Since the regression method uses only observed data to estimate regression parameters for the MI, only control subjects are used for the imputation of missing values at Week 24/ET in the active treatment groups.

Step 3: Reassemble (concatenate) datasets (REST_V6, IMPUTED_V6).

The final, reassembled dataset will include M=40 imputations of all subjects with missing data at Week 24/ET imputed using J2C method. This dataset, labeled *EFF_MI_J2C* for reference, is used in the statistical analysis described in Section 10.4.

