7.1.5 Estimator and Estimation Method - Primary Efficacy Analysis

Estimator and estimation method (CSNS): For the co-primary endpoint CSNS, the estimator is the mean difference between treatments (active versus placebo) in change from baseline to the end of Week 4 in the 7-day average instantaneous AM CSNS. Estimation is based on a mixed-effects model for repeated measures (MMRM) where changes from baseline to Week 2 and Week 4, in the 7-day average instantaneous AM CSNS, respectively, are the repeated measures. The 7-day windows used to define the 7-day average instantaneous AM CSNS from baseline through Day 84 (Week 12) are provided in Section 9.1.2.1, Table 9.1. The MMRM model will employ Restricted Maximum Likelihood (REML) for parameter estimation and the Kenward-Roger method for calculating the denominator degrees of freedom. An unstructured covariance matrix will be used to estimate within-subject error. For the treatment policy estimand, (reference Section 7.1.3, criteria 3,c), missing data due to study discontinuation will be estimated within the MMRM model under the assumption that the missing data are missing at random (MAR) and that early discontinuation from the study (prior to Week 4) is unlikely to reflect a treatment effect. Contingencies in the event of an issue with MMRM model convergence are described in Section 10.5.

The MMRM model will include categorical effects for previous sinus surgery (Y,N), nasal polyp status (present, absent), treatment (OPN-375 186 µg, OPN-375 372 µg, placebo), Week (2, 4), treatment-by-day interaction, and the continuous covariate: baseline 7-day average total instantaneous AM CSNS, with baseline-by-day interaction. The model-based LS mean difference between each active treatment group and placebo (active-placebo), 95% CI, and p-value will be displayed.

Estimator and estimation method (APOV): For the co-primary endpoint APOV, the estimator is the mean difference between treatments (active versus placebo) in the change from baseline to Week 24/ET APOV. Estimation is based on an ANCOVA model including categorical effects for previous sinus surgery (Y, N), nasal polyp status (present, absent), treatment (OPN-375 186 µg, OPN-375 372 µg, placebo), and baseline APOV. The model-based LS mean difference between each active treatment group and placebo (active-placebo), 95% CI, and p-value will be displayed.

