7.8 Subgroup Analyses

The following endpoints will be analyzed according to the primary estimand for the following stratification subgroups:

1. Subjects with versus without polyps at baseline
2. Subjects with versus without prior sinus surgery at baseline

These subgroups are defined based on a subject's actual polyp status and actual nasal surgery status at baseline.

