7.8.5 Subgroup Analysis of POV in the Worst Sinus

- c) change from baseline to Week 24/ET in WPOV
- d) change from baseline to Week 24/ET in WPOV-E
- e) change from baseline to Week 24/ET in WPOV-M
- f) change from baseline to Week 24/ET in WZLM

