7.8.6 Models for Subgroup Analyses

The primary estimand and models described in described in Sections [7.1.3-7.1.5](#) will also include the appropriate terms for treatment-by-subgroup interaction as well as the appropriate contrasts to obtain the within-subgroup inferential statistics. The model-based, within-subgroup LS mean difference between each active treatment group and placebo (active-placebo), 95% CI, and nominal p-value will be displayed, as well as the treatment-by-subgroup interaction nominal p-value.

For the APOV endpoint, the subgroup analysis will be based on the same MI dataset created for the primary analysis.

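### SAP 10.2 Step 2 imputes missing active-arm values from baseline alone, leaving out the polyp and surgery factors that its own placebo step, the primary APOV model and the subgroup analyses use (minor)

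*SAP*

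**What the plan says.** SAP 10.2 uses two imputation models in sequence. Missing placebo values are first imputed under MAR with treatment and "baseline covariate, nasal polyp status (present, absent), previous sinus surgery (Y, N"). Step 2 then imputes missing active-arm values, fitted in control subjects only, "using a regression of Week 24/ET analysis variable on baseline value of endpoint only". The section applies this to a list of endpoints that opens with "variables: APOV, WPOV-E, WPOV-M, WPOV; LM, ZLM, and WZLM scores".

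The primary APOV model in SAP 7.1.5 carries both factors: "Estimation is based on an ANCOVA model including categorical effects for previous sinus surgery (Y, N), nasal polyp status (present, absent"). SAP 4.4 likewise puts both stratification factors in the analysis model.

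The subgroups in SAP 7.8 are defined by "actual polyp status and actual nasal surgery status at baseline". SAP 7.8.6 says the models "will also include the appropriate terms for treatment-by-subgroup interaction", and adds: "For the APOV endpoint, the subgroup analysis will be based on the same MI dataset created for the primary analysis". That last sentence names APOV only. However, WPOV, WPOV-E, WPOV-M and WZLM are also imputed through Step 2 and analysed by subgroup (SAP 7.8.5, for example "change from baseline to Week 24/ET in WZLM").

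**The concern.** An imputation model should contain at least the variables that the analysis will interact with treatment. Step 2 leaves out exactly those two, and the SAP text gives no reason.

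Consider a placebo and an active subject who both have polyps, the same baseline and a missing endpoint. The placebo subject is imputed with polyp status taken into account. The active subject is imputed towards the mean of all placebo subjects. Unless placebo outcomes are the same in both strata at equal baseline, this creates a difference within the stratum that jump-to-control does not intend. Jump-to-control requires treatment to be left out of Step 2; it does not require the baseline strata to be left out.

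What is at stake is the APOV effect by polyp status and by prior surgery, which is a listed secondary endpoint (protocol 3.2.1.3, SAP 3.4.3), together with the interaction p-value reported beside it. The tipping-point analysis starts from the MAR dataset and the observed-cases analysis does no imputation, so neither uses Step 2. Neither is specified by subgroup, so they do not check this.

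**Working it through.** **Inputs from the documents.** 111 per arm, APOV difference −11.3, SD 27, two-sided 5%, 88% power (SAP 4.2); 40 imputations (SAP 10.1). The polyp share lies between the 50% cap (SAP 3.1) and (333 − 125)/333 = 62.5% (protocol 3.3); 60% is used below.

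**The plan's own figure.** SE = 27 × √(2/111) = 3.62. Power = Φ(11.3/3.62 − 1.96) = 87.7%, which reproduces the stated 88%. The documents give no figure for the imputation model itself.

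**Assumptions.** The documents give no dropout rate and no placebo gap by stratum. Let m be active-arm missingness (5% to 20%), g the placebo gap between strata at equal baseline (5 to 10 points), p the polyp share, and r the correlation of the factor with baseline. The true effect is −11.3 in both strata, so the true interaction is 0. Placebo subjects with polyps are taken to improve more; the reverse flips every sign.

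**Formulas (r = 0).**
- Effect with the two factors in Step 2: −11.3 × (1 − m) in both strata.
- Shift as written: +m(1 − p)g with polyps, −m·p·g without.
- Interaction shift: m·g. With r ≠ 0 it is m·g·(1 − r²); r = 0.3 lowers it by 9%.

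Worked case, m = 10%, g = 10: −11.3 × 0.9 = −10.17. The shifts are +0.10 × 0.4 × 10 = +0.4 and −0.10 × 0.6 × 10 = −0.6. As written this gives −9.77 and −10.77, an interaction of 1.0.

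The closed form was checked by simulating SAP 10.2 and 10.4: 750 trials per scenario, 40 imputations, three arms of 111, residual SD 27, Rubin's rules.

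| m | g | m·g | With factors, both strata | As written, polyps | As written, no polyps | Simulated interaction shift (Monte Carlo SE) | Shift / Rubin SE |
|---|---|---|---|---|---|---|---|
| 5% | 5 | 0.25 | −10.74 | −10.64 | −10.89 | 0.24 (0.02) | 0.25/7.71 = 0.03 |
| 5% | 10 | 0.50 | −10.74 | −10.54 | −11.04 | 0.49 (0.02) | 0.50/7.71 = 0.06 |
| 10% | 10 | 1.00 | −10.17 | −9.77 | −10.77 | 0.99 (0.03) | 1.00/7.95 = 0.13 |
| 20% | 10 | 2.00 | −9.04 | −8.24 | −10.24 | 1.99 (0.05) | 2.00/8.39 = 0.24 |

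Interaction rejection rates at nominal 5%, as written, were 3.7%, 4.0%, 2.4% and 2.3% in the same order, so there is no inflation.

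**Second simulation.** This used 1,000 trials, 10 imputations, 62.5% with polyps and the opposite gap direction. With baseline only versus baseline plus both factors, the interaction was −1.17 versus −0.19 at 10%/10, and −2.20 versus −0.16 at 20%/10. The shifts, −0.98 and −2.04, match the formula.

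**Prior surgery.** The same formula applies. With m = 10%, g = 10 and an assumed 30% with prior surgery, the shifts are +0.7 and −0.3, an interaction of 1.0 (simulated 1.05, Monte Carlo SE 0.04).

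**Overall APOV estimate.** Shift = p(1 − p)(m_polyp − m_no polyp)g. With equal dropout this is 0 (simulated within 0.02). With 20% versus 10% dropout and g = 10 it is 0.6 × 0.4 × 0.10 × 10 = 0.24 points, or 0.24/3.62 = 0.07 SE (simulated 0.23). In the second simulation, with active-arm dropout 3:1 in polyp subjects and g = 10, it moved by 10.36 − 10.14 = 0.22 at 10% missing and 9.53 − 9.11 = 0.42 at 20%.

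**The case against.** The case against has five parts.

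**No contradiction.** The protocol leaves imputation detail to the SAP, and a baseline regression fitted in all controls can be read as giving active subjects the control arm's profile. Section 10.2 also cites a textbook chapter that is not available here, so whether that source uses baseline only cannot be checked. This stands: the point is an imputation model poorer than the analysis model, not a conflict between documents.

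**Negligible size.** Both drivers are assumed, and the documents suggest low missingness. Subjects who withdraw are asked back for a CT (protocol 6.5), Week 24/ET is the last non-missing value (SAP 9.1.5), steroid and surgery events receive poor scores (SAP 7.1.3), and missing information is expected to be small (SAP 10.1). This also stands. The 20% rows are an extreme, and 0.25 to 0.5 points is the more likely range.

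**Truncation.** SAP 10.1 truncates imputed values to the variable's range, which the closed form ignores. A further simulation gave interaction shifts of 0.27, 0.96 and 2.04 without truncation, and 0.23, 0.88 and 1.73 with it, at 5%/5, 10%/10 and 20%/10. Truncation trims the figures but does not remove the shift.

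**Which strata.** Subgroups use actual status (SAP 7.8), while the primary analysis uses status as stratified (SAP 4.4). The change must say which enters Step 2. This matters only for mis-stratified subjects.

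**No conclusion changes.** Subgroup p-values are nominal and outside the testing hierarchy. This is agreed, and it is why the point is rated minor.

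**Conclusion.** The concern holds and is minor. Followed as written, Step 2 shifts the polyp and surgery subgroup effects in opposite directions whenever placebo change differs by stratum at equal baseline. The direction depends on the sign of that gap, which the documents do not give. Under the assumed ranges the APOV interaction is off by 0.25 to 2.0 points, never more than about a quarter of its standard error. The same mechanism applies to WPOV, WPOV-E, WPOV-M and WZLM, although their shifts were not computed. The primary APOV conclusion, planned sample size and power are unaffected. Confidence is high on the text and the mechanism; the size rests on the assumed missingness and gap.

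**What to change.** In SAP 10.2 Step 2, regress the Week 24/ET value on baseline value, nasal polyp status and previous sinus surgery, keeping control subjects as the only source of the parameters. State whether as-stratified or actual status is used, and use the same version in both imputation steps.

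The cost is one model statement. Both factors are already collected for randomisation, so no new data or subjects are needed. The edit alters the dataset behind the primary APOV analysis, so it should be made before unblinding; after that, it should be reported as a labelled supplementary analysis.

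Optional, for consistency only: the rank analysis (SAP 7.2.2, protocol 9.4.1) includes previous sinus surgery but not polyp status, and adding it would match the primary model. No bias is claimed there and no precision gain was computed.

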10.3 Multiple Imputation Method – Tipping Point

Tipping Point analyses will be conducted using the sequential modeling method as described in, (O'Kelly & Ratitch, 2014), Chapter 7, and specifically the third (sequential) approach described Section 7.4.7 of the book. First, the initial analysis dataset is used to impute missing data in the control group with multiple imputation under MAR assumption; the MI is performed as described above in Section 10.2 and dataset *EFF_MI_MAR* is used as the input dataset to the Tipping Point analysis.

The Tipping Point analysis will then be performed on the *PEFF_MI_MAR* dataset. A constant, δ , will be applied to the imputed values in the active treatment groups; δ will be defined in units of the within-group standard deviation (σ) of change from baseline in APOV; that is, $\delta = c \cdot \sigma$, where the constant c is a fraction. An estimate of σ will be obtained from the root mean square error (RMSE) of the primary analysis model described in Section 7.1.5. To find the tipping point, the sequence of fractions $c = 0.25, 0.50, 0.75, 1.0$, and so on in 0.25 increments, will be chosen until the tipping point is reached. However, this search will employ an efficient numerical searching algorithm to find the Tipping Point value δ^* . Since the APOV endpoint has a range from 0-100, imputed values with δ added cannot exceed the maximum value of 100. Therefore, any imputed values with δ added that exceed the maximum score of 100 will be assigned the maximum score of 100.

Note that it is possible a Tipping Point does not exist. If the Tipping Point is not reached for value of δ such that all missing data in the active treatment groups are assigned the maximum score, then a Tipping Point does not exist.

The output dataset for the Tipping Point analysis will be labelled *PEFF_MI_TP_D* for reference, where D will represent the current value of δ in the search.

10.4 Multiple Imputation – Statistical Analysis and Inference

Statistical Analysis

The ANCOVA statistical model for the primary efficacy analysis described in Section 7.1.5 will be used to analyze the MI dataset *EFF_MI_J2C* (primary analysis) and *MI_PEFF_TP_D* (Tipping Point sensitivity analysis). The statistical analysis is performed separately on each of the M=40 complete datasets. The summary statistics resulting from these analyses are output to SAS ODS datasets: DIFFS (least squares mean (LSM) estimates of differences between treatments), LSMEANS (LSM estimates for each treatment group, and SOLUTIONF (model parameter estimates). Note the SAS PROC MI procedure produces a SAS variable *_Imputation_*; this SAS variable identifies each of the M=40 MI datasets for analyses and inference.

Statistical Inference

The statistical method for combining the summary statistics obtained from the statistical analysis of each of the M=40 MI datasets is well established (Rubin's method); it is based on obtaining an overall estimate of mean and variance from these MI summary statistics, forming a test statistic for the hypothesis test and estimating the degrees of freedom, and obtaining a p-value and a confidence interval for formal statistical inference. Rubin's method is described in (O'Kelly & Ratitch, 2014), Chapter 6, Section 6.4.

This method is implemented in SAS PROC MIANALYZE; the procedure is designed to accept the SAS ODS output from the statistical analysis. If the unadjusted degrees of freedom is very large compared to the complete-data degrees of freedom, then adjusted degrees of freedom will be used.

10.5 MMRM Model convergence contingencies

Model convergence is not anticipated to be an issue with the linear and logistic MMRM models used for the analysis of data from this trial; however, in the event a convergence issue arises for any analyses, in each case, both a heterogeneous Toeplitz and Toeplitz covariance structure will be considered in sequence in place of the unstructured covariance. In this case, the empirical sandwich estimator will be used as a sensitivity analysis to correct for potential model misspecification.

11 CHANGES FROM THE PROTOCOL

The following changes were made to this SAP post Protocol Amendment 6.0.

Section 3.3.3 and 3.4.3 (Objectives and Endpoints)

The following objectives and secondary endpoints were added:

- change from baseline to Week 24/ET in APOV in the ethmoid sinuses (APOV-E)
- change from baseline to Week 24/ET in APOV in the maxillary sinuses (APOV-M)
- change from baseline to Week 24/ET in APOV in the ethmoid sinuses (APOV-E) for CRS with NP and without NP sub-groups and in subjects with and without previous sinus surgery
- change from baseline to Week 24/ET in APOV in the maxillary sinuses (APOV-M) for CRS with NP and without NP sub-groups and in subjects with and without previous sinus surgery
- change from baseline in the volume of the nasal cavity opacified

The following objective and secondary endpoint was removed:

- percent of subjects requiring rescue medication after Week 4

Section 7.2 Sensitivity Analyses

- Section 7.2.3 Added an Observed Cases Sensitivity Analysis

Section 7.5.3 and Section 9.3.2 (Percentage of Opacified Volume)

- Clarified the definition of WPOV, WPOV-E, WPOV-M and the corresponding endpoints
- Added the definition of APOV-E and APOV-M and the corresponding endpoints

Section 7.5.4 and Section 9.3.6 (Qualitative CT Scan Assessment)

- Clarified the definition of WZLM and the corresponding endpoints

13 APPENDICES

13.1 Appendix 1: PSQI Scoring

Scoring the PSQI

The order of the PSQI items has been modified from the original order in order to fit the first 9 items (which are the only items that contribute to the total score) on a single page. Item 10, which is the second page of the scale, does not contribute to the PSQI score.

In scoring the PSQI, seven component scores are derived, each scored 0 (no difficulty) to 3 (severe difficulty). The component scores are summed to produce a global score (range 0 to 21). Higher scores indicate worse sleep quality.

Component 1: Subjective sleep quality—question 9

Response to Q9	Component 1 score
Very good	0
Fairly good	1
Fairly bad	2
Very bad	3

Component 1 score: _____

Component 2: Sleep latency—questions 2 and 5a

Response to Q2	Component 2/Q2 subscore
≤ 15 minutes	0
16-30 minutes	1
31-60 minutes	2
> 60 minutes	3

Response to Q5a	Component 2/Q5a subscore
Not during past month	0
Less than once a week	1
Once or twice a week	2
Three or more times a week	3

Sum of Q2 and Q5a subscores	Component 2 score
0	0
1-2	1
3-4	2
5-6	3

Component 2 score: _____

Component 3: Sleep duration—question 4

Response to Q4	Component 3 score
> 7 hours	0
6-7 hours	1
5-6 hours	2
< 5 hours	3

Component 3 score: _____

Component 4: Sleep efficiency—questions 1, 3, and 4

Sleep efficiency = (# hours slept/# hours in bed) X 100%

hours slept—question 4

hours in bed—calculated from responses to questions 1 and 3

Sleep efficiency	Component 4 score
> 85%	0
75-84%	1
65-74%	2
< 65%	3

Component 4 score: _____

Component 5: Sleep disturbance—questions 5b-5j

Questions 5b to 5j should be scored as follows:

Not during past month	0
Less than once a week	1
Once or twice a week	2
Three or more times a week	3

Sum of 5b to 5j scores	Component 5 score
0	0
1-9	1
10-18	2
19-27	3

Component 5 score: _____

Component 6: Use of sleep medication—question 6

Response to Q6	Component 6 score
Not during past month	0
Less than once a week	1
Once or twice a week	2
Three or more times a week	3

Component 6 score: _____

Component 7: Daytime dysfunction—questions 7 and 8

Response to Q7	Component 7/Q7 subscore
Not during past month	0
Less than once a week	1
Once or twice a week	2
Three or more times a week	3

Response to Q8	Component 7/Q8 subscore
No problem at all	0
Only a very slight problem	1
Somewhat of a problem	2
A very big problem	3

Sum of Q7 and Q8 subscores	Component 7 score
0	0
1-2	1
3-4	2
5-6	3

Component 7 score: _____

Global PSQI Score: Sum of seven component scores: _____
